The benefits of AVF over AVG are least certain in older adults, as age-related biological changes independently modulate patient outcomes.¹⁰ Nationally representative cohort studies of older adults with incident ESKD have shown similar patient survival between those whose first AV access placed or used was a fistula or a graft.^{11,12} Compared with grafts, fistulas fail more often and necessitate longer times and more subsequent procedures to aid development, exposing older patients to time-consuming procedures that may negatively affect upper extremity strength and erode their quality of life.¹³⁻¹⁶ Hitherto, the contribution of pre-operative muscle strength to AV access outcomes and the impact of AV access placement on upper extremity strength and self-sufficiency have not been evaluated. We propose a randomized pilot trial in older adults with pre-dialysis advanced chronic kidney disease (CKD) or incident ESKD using a TCVC for HD who had no prior AV access surgery and have upper extremity vasculature suitable for either fistula or graft placement. Participants will be randomized to receive an upper extremity AVF-first or AVG-first access for HD.

Objectives

The primary objective of this study is to prospectively evaluate patient and vascular access outcomes in a randomized intervention and in a patient population in whom fistula-first guidelines have been applied despite the lack of proven benefit and at the detriment of more access failures and procedures. Our hypothesis is that there is a bidirectional relationship between the type of first AV access and patient outcomes as follows: a) the graft-first strategy will confer a more effective transition from TCVC-based to AV access-based HD and will limit upper extremity functional impairment from protracted access development and subsequent access procedures, and b) preoperative muscle strength will impact AVF development.

Methods and Measures

Design

This randomized pilot trial will be parallel-arm in design (Appendix A). We plan to enroll 50 patients of age ≥ 65 years, with incident ESKD or advanced CKD expected to require HD initiation within 90 days of screening. Screening for potential participants will be performed

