in two stages. In the first stage, all patients ≥ 65 years old receiving chronic HD and use a TCVC will be screened for eligibility. Of these patients, only those who did not have a previous AV access surgery and are considered for AV placement (according to goals of care established by the patient's nephrologist) will be maintained as potential participants and advanced to the second phase of screening pending determination of surgical eligibility for placement of upper extremity AVF and AVG. Ultrasound vascular mapping of both upper extremities to assess vascular anatomy is routinely performed pre-operatively at our institution. Arterial diameter of ≥ 2 mm and vein diameter of ≥ 2.5 mm at the site of AV anastomosis indicate suitability for AVF surgical creation.⁷ To complete the eligibility criteria, patients must have proper anatomy (in either upper extremity) for placement of AVF (forearm or arm) and AVG (forearm or arm).

Setting

Participant recruitment will occur at Wake Forest Baptist Medical Center (WFBMC) Outpatient Nephrology Clinics, WFBMC Inpatient Nephrology Service, Wake Forest Outpatient Dialysis (WFOPD) units or any other Wake Forest affiliated institution (i.e., High Point Regional Medical Center).. After the screening process identifies a potential study candidate, the patient will be approached for study participation. The study coordinator and/or the PI and/or other study member will contact the patient and present an overview of the study. This will be done either in person, by phone, or electronically (e.g., Skype or Facetime). When the patient presents interest in the study after the initial overview, the study coordinator and/or the PI or other study team member will meet in person with the potential study participant to further review the study and the informed consent to patient's and/or patient's family member/representative full understanding, and finalize the enrollment.

Subjects selection criteria

The overall eligibility will be reached as a consensus between the PI and the vascular surgeon.

Inclusion Criteria

1. Age ≥ 65 years

2. Incident ESKD on chronic HD and recovery of kidney function is unlikely or advanced CKD expected to require HD initiation within 90 days of screening and deemed medically necessary by the treating nephrologist to proceed with AV access placement (either AVF or AVG) in preparation for HD initiation
3. TCVC is the sole vascular access used for HD

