4. Did not undergo AV access placement in the past
5. Medically eligible to receive AVF or AVG placement as deemed by the treating nephrologist
6. Surgically eligible to receive either an AVF or an AVG
7. HD is the intended long-term modality of treatment for ESKD
8. Planning to remain within Wake Forest provided health care for at least 12 months

Exclusion Criteria

1. Presence of an AVF or AVG
2. Previous attempt(s) for AV vascular access placement
3. Native vasculature not suitable for placement of AV access
4. Imminent transplant planned (within 6 months)
5. Anticipated life expectancy <9 months

This study targets elderly population with advanced CKD and ESKD; therefore, the clinical scenario of when an elderly individual is not able to consent for himself or herself will not be uncommon. Because the study objectives will not be met without including these subjects, this study plans to enroll elderly subjects who are not able to consent for themselves. The foreseeable risks to these subjects in this study are low as is the negative impact. For elderly with impaired mental capacity, permission for study participation will be obtained from the subject's Legally Authorized Representative (LAR).

Sample Size

This pilot trial has the principal aim of testing the feasibility of randomizing initial AV access placement to an upper extremity AVG-first (intervention) or AVF-first (comparator) strategy in patients ≥ 65 years of age. For this goal, we plan to enroll 50 participants (25 per arm).

Interventions and Interactions

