Screening for potential participants will be performed in two stages. In the first stage, all patients ≥ 65 years old who have pre-dialysis CKD or have ESKD receiving chronic HD will be screened for eligibility. Of these patients, only those who did not have a previous AV access surgery and are considered for AV placement (according to goals of care established by the patient's nephrologist) will be maintained as potential participants and advanced to the second phase of screening pending determination of surgical eligibility for placement of upper extremity AVF and AVG. Ultrasound vascular mapping of both upper extremities to assess vascular anatomy is routinely performed pre-operatively at our institution. Arterial diameter of ≥ 2 mm and vein diameter of ≥ 2.5 mm at the site of AV anastomosis indicate suitability for AVF surgical creation.⁷ To complete the eligibility criteria, patients must have proper anatomy (in either upper extremity) for placement of AVF (forearm or arm) and AVG (forearm or arm). After written informed consent is obtained, participants will be allocated with equal probability to either a graft-first (intervention) or fistula-first (comparator) strategy. Allocation to AVG or AVF will be done using randomly permuted blocks of varying sizes to maintain balance between the groups.

Demographic and medical data will be collected from all participants, using direct patient interview and electronic medical records. Following randomization, collected data is derived from standard of care and from assessments specifically conducted as part of this study.

Study-specific assessments will include muscle strength (assessed with upper arm grip-strength test in each arm using a hand-held dynamometer)¹⁷, four-meter gait speed (4MGS)
¹⁸(HealthMeasures. NIH Toolbox training manual English version.

Available at: <http://www.healthmeasures.net/images/nihtoolbox/>

[Training-Admin-Scoring_Manuals/NIH_Toolbox_Training_ManualEnglish_9-25-12.pdf](http://www.healthmeasures.net/images/nihtoolbox/Training-Admin-Scoring_Manuals/NIH_Toolbox_Training_ManualEnglish_9-25-12.pdf)

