Appendix D. Vascular access outcomes

Vascular access outcomes (according to the recommendations of the Committee on Reporting Standards for Arteriovenous Accesses, Society for Vascular Surgery and American Association for Vascular Surgery)	
AV access outcome	Definition
Primary access failure	Permanent failure of the fistula or graft before hemodialysis suitability. This includes inadequate maturation, thrombosis, failure of first and subsequent cannulations, and other complications leading to nonfunctional fistula or graft.
Successful cannulation	The arteriovenous access became the primary vascular access for hemodialysis (the fistula or graft access has been cannulated with two 16- or 15-gauge needles for ≥ 3 consecutive dialysis sessions and the TCVC was removed).
Suitability for hemodialysis	Fistula or graft use with two needles and maintenance of blood flow $\geq 300\text{ml}/\text{min}$ for $\geq 75\%$ of dialysis sessions over a continuous 4-week. The maturation criteria can be satisfied at any time within 6 months of fistula or graft creation surgery.
Unassisted access maturation	Criteria for fistula or graft suitable for hemodialysis (based on the above criteria) are met before any endovascular or secondary surgical procedure to facilitate maturation.
Assisted access maturation	Satisfaction of the criteria for fistula or graft suitability for hemodialysis after a procedure to facilitate maturation (e.g., angioplasty, stent placement, surgical revision, ligation of accessory veins).
Primary access patency	Intervention-free access survival defined as the time from fistula or graft creation to any intervention to maintain patency.
Secondary access failure	Permanent failure after the fistula or graft met dialysis suitability criteria with subsequent abandonment.
Noninfectious complications	Stenosis, thrombosis, hand ischemia, aneurysm, pseudoaneurysm, infiltration.
Infectious complications	Fistula or graft cellulitis, abscess, bacteremia.
Access procedures	Angioplasty, stent placement, surgical revision, ligation of accessory veins, superficialization of vein.
Other clinical outcomes	TCVC placement, new AV access surgical creation, AV access-related hospitalization or death.
Limb ischemia following AV access placement	
Symptoms	Paresthesia, pain, hand stiffness, ulceration and tissue loss in the limb with arteriovenous access.

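### Between-arm access comparisons take no account of dialysis status at randomization, so a chance imbalance could shift them by several points; adjust for it in the analysis.

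*Combined protocol and SAP*

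**What the plan says.** **Allocation.** Under Interventions and Interactions, "participants will be allocated with equal probability to either a graft-first (intervention) or fistula-first (comparator) strategy", and "Allocation to AVG or AVF will be done using randomly permuted blocks of varying sizes to maintain balance between the groups". No stratification factor appears there or elsewhere. The one use of the word stratified, in the Analytical Plan, refers to splitting quality-of-life outcomes by arm.

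**Population.** The Objectives and Methods text describes two kinds of patient. The end of the Background gives the population as "older adults with pre-dialysis advanced chronic kidney disease (CKD) or incident ESKD using a TCVC for HD". The Design section plans to enroll older patients "with incident ESKD or advanced CKD expected to require HD initiation within 90 days of screening". Inclusion criterion 2 repeats the route for "advanced CKD expected to require HD initiation within 90 days of screening", and Interventions and Interactions says "all patients ≥ 65 years old who have pre-dialysis CKD or have ESKD receiving chronic HD will be screened for eligibility".

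**Conflicting wording.** Inclusion criterion 3 requires a tunneled central venous catheter (TCVC) to be the only access in use for hemodialysis (HD). The first screening stage in the Design section covers only HD patients with a TCVC. Subject Recruitment Methods lists TCVC use as an additional requirement. Read literally, these three places leave no room for a patient not yet on dialysis.

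**Outcomes.** Appendix D counts cannulation as successful when the access has been "cannulated with two 16- or 15-gauge needles for ≥ 3 consecutive dialysis sessions and the TCVC was removed". Suitability for hemodialysis needs two-needle use at adequate flow over four continuous weeks, within 6 months of the creation surgery.

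**Analysis.** The Analytical Plan compares arms by robust regression and non-parametric methods and names no covariate. The HD start date is among the data collected at enrollment.

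**The concern.** Permuted blocks equalize the number of patients per arm, not their composition. Dialysis status is known at randomization, and its link to the use-based outcomes comes from the protocol's own definitions. A patient who has not started HD cannot be cannulated for dialysis or meet the suitability rule. The suitability clock runs from surgery, not from HD start, so time before dialysis uses up the 6-month window. Catheter complications can occur only in someone who has a catheter.

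If one arm happens to receive more pre-dialysis patients, its cannulation, suitability and catheter results will differ for reasons unrelated to access type. These outcomes bear on the hypothesis in the Objectives that graft-first gives a more effective move away from catheter dialysis. The Analytical Plan also says the pilot results will inform a larger trial, so a distorted difference could be carried forward.

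**Working it through.** **1. The plan's own figure.** The only computed design figure is the maximum error margin of 0.138 at p = 0.5. With n = 50: 1.96 × √(0.5 × 0.5 / 50) = 0.1386, which is 0.138 truncated. It reproduces. It describes single proportions over all participants, not arm differences; the documents give no power or precision for those.

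**2. Inputs.** From the documents: 50 participants, 25 per arm, 1:1 allocation. Assumed, because the documents do not give them: the pre-dialysis share q, and the gap in outcome rate between patients on HD and pre-dialysis patients.

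**3. Chance of imbalance.** Treat the number of pre-dialysis patients in each arm as an independent Binomial(25, q). A difference of 5 of 25 is 20 percentage points.

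| q | P(difference ≥ 4) | P(difference ≥ 5) |
|---|---|---|
| 10% | 0.096 | 0.034 |
| 20% | 0.213 | 0.110 |
| 30% | 0.279 | 0.164 |
| 50% | 0.322 | 0.203 |

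If instead the total K of pre-dialysis patients among the 50 is held fixed (hypergeometric), the chance of a difference of at least 5 is 0.050, 0.074, 0.217, 0.148 and 0.258 for K = 5, 10, 15, 20 and 25. The sequence is uneven because the difference between arms must be odd when K is odd and even when K is even. The order of magnitude is the same.

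**4. Size of the shift.** Shift = imbalance × outcome gap. For a 20-point imbalance:
- gap 20 points: 0.20 × 0.20 = 0.04, or 4 points;
- gap 40 points (for example 70% against 30%): 0.20 × 0.40 = 0.08, or 8 points.

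**5. Scale.** The 95% half-width of an unadjusted arm difference is 1.96 × √(2p(1 − p)/25). With 70% and 30% outcomes, the overall rate p is 0.62, 0.58 and 0.50 at q = 20%, 30% and 50%, giving half-widths of 26.9, 27.4 and 27.7 points. Over all possible randomizations, the SD of the shift is 0.40 × √(2q(1 − q)/25) = 4.5, 5.2 and 5.7 points. The share of the variance of the arm difference that comes from dialysis status is 0.40² × q(1 − q) / [p(1 − p)], which is 11% at q = 20% and 16% at q = 50%.

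**6. Effect on error rates, and what adjustment does.** Trials were simulated with no treatment effect: 12,000 per scenario, q = 20%, 40% and 50%, gaps of 20 and 40 points, and assumed block sizes of 2, 4 and 6.

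| Plain blocks | Type I error at nominal 5% |
|---|---|
| All trials, unadjusted | 5.4% to 6.4% |
| Imbalance ≥ 20 points, unadjusted, gap 20 | 6.3% to 8.5% |
| Imbalance ≥ 20 points, unadjusted, gap 40 | 9.1% to 11.0% |
| Imbalance ≥ 20 points, Cochran-Mantel-Haenszel by dialysis status | 3.5% to 5.4% |

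The mean arm difference over all trials was about zero. With blocks stratified by dialysis status, the SD of the imbalance fell from 11–14 points to about 3, and no trial reached a 20-point imbalance.

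**The case against.** The strongest reply is that this is a feasibility pilot. The Sample Size section makes feasibility the principal aim. The targets in the Analytical Plan, at least 70% consenting and at least 70% having surgery within 90 days, are proportions over everyone, so imbalance between arms cannot distort them. That stands. It does not dispose of the point, because the Objectives section names access outcomes as what the study sets out to evaluate.

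Second, the arm comparisons listed explicitly are grip strength, pain, satisfaction, independence and quality of life. No specific test of cannulation, suitability or catheter outcomes is written. That also stands: these outcomes are covered only by the general sentence on comparing arms.

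Third, the shift is small against sampling noise, and any prognostic factor can be unbalanced in 50 patients. The unadjusted interval already allows for such variation on average. This is correct, and it limits the weight of the point. What sets dialysis status apart is that Appendix D builds it into the outcomes.

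Fourth, the pre-dialysis share may be close to zero if the catheter criteria are read literally, and the outcome gap may narrow because HD is expected within 90 days of screening and follow-up lasts at least 12 months. Both are possible; the documents settle neither.

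Fifth, neither stratification nor adjustment repairs an outcome that a patient who never has a catheter cannot meet as worded. That is true, and it is a separate matter of definition.

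A reader might infer that the randomization is biased, or that the trial is invalid without stratified blocks. The documents support neither: allocation is properly random, and adjustment alone controls the conditional error.

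**Conclusion.** The point holds as a modest one about analysis. The plan mixes patients on and off dialysis, defines key access outcomes that depend on being on dialysis, and neither balances nor adjusts for that status. If a 20-point imbalance occurs, the access comparisons shift by 4 to 8 points, and a nominal 5% test has a true error of roughly 6% to 11%. The chance of such an imbalance is 3% to 20% for pre-dialysis shares of 10% to 50%.

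These sizes rest on an assumed share and an assumed outcome gap. They also rest on reading the eligibility text as admitting pre-dialysis patients, as criterion 2 and the Interventions section do.

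It would be tempting to conclude that chance imbalance could produce a convincing false difference between graft-first and fistula-first. The figures do not support that: an 8-point shift is well inside a half-width of about 27 points.

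**What to change.** **Main change.** In the Analytical Plan, state that between-arm comparisons of access and catheter outcomes will include dialysis status at randomization (on HD with a TCVC, or pre-dialysis) as a covariate or stratum, and that this status will be tabulated by arm. It can be derived by comparing the HD start date with the randomization date. The cost is one binary term or stratum and no new data. If very few pre-dialysis patients enroll, the term will be imprecisely estimated and will matter little.

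**Optional, only if enrollment has not begun.** In Interventions and Interactions, stratify the permuted blocks by the same factor. This needs two lists instead of one. Arm totals may end slightly unequal, by up to half a block per stratum; the block sizes are not stated, so the amount cannot be given.

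**Reconcile.** Inclusion criterion 3, the first screening stage in the Design section and the TCVC requirement in Subject Recruitment Methods must be brought into line with criterion 2, the population stated at the end of the Background and the screening text in Interventions and Interactions. If the outcome is that pre-dialysis patients are not eligible, neither change above is needed.

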Accessed November 16, 2018), satisfaction with the vascular access (using the short-form vascular access questionnaire [SF-VAQ])¹⁹, pain at the AV access site (using the Verbal Descriptor Scale [VDS] or the modified Abbey Pain Scale [mAPS] for people who cannot verbalise)^{20;21}, level of independence (using activities of daily living [ADL] and independent ADL [IADL] instruments)^{22;23}, and health-related quality of life (using the Kidney Disease Quality of Life instrument short form [KDQOL-SF] version 1.3. which consists of a generic core (Short Form-36 [SF-36]) and an 11-item kidney disease-specific scale).²⁴, participant's

individual study experience (study conduct, intervention outcomes, and intervention decisions) (using the Qualitative Study Interview designed by the PI and safety monitor). The assessment instruments (SF-VAQ, mAPS, ADL, IADL, KDQOL-SF) are summarized in Appendix B. The schedule of assessments is summarized in Appendix C.

Data Collection and Outcome Measure(s)

Data collection at enrollment: sociodemographic characteristics (age, sex, race, marital status, educational level, living arrangement); health behaviors (smoking and alcohol consumption [no, formerly, or yes]); ESKD etiology; date of HD commencement; and pre-dialysis care (first nephrology clinic visit and number of clinic visits prior to the first HD date); Charlson comorbidity index (CCI); medications (lipid lowering drugs, anticoagulants, antiplatelets); upper limb muscle strength assessed with grip-strength test in each arm using an isometric dynamometer; gait speed. The grip-strength test will be performed twice on each hand for each assessment and the mean of the two results will be used for statistical analyses; a cut-off point <16 kg in women and <26 kg in men will define muscle weakness. The four meter gait speed (4MGS) will be assessed on a flat, unobstructed four meter delineated course by trained research staff following a standard operating procedure.

Data regarding arterial and venous diameters on pre-operative ultrasound mapping, AV access date of placement, and location of AV anastomosis will be recorded for each participant. Results of blood work obtained on a monthly basis (per standard care) at the outpatient dialysis units. This includes measurements of dialysis adequacy, anemia management, and bone-mineral metabolism.

Vascular access outcomes.

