We will begin by examining descriptive statistics (means, standard deviations, minima, quartiles, maxima) and plots of the data (histograms and boxplots) to become familiar with the data and check for outliers. The proportion of people meeting each of the feasibility and protocol adherence endpoints with accompanying 95% confidence intervals (CI) will be calculated using skew-corrected score tests with a continuity correction. The maximum uncorrected error margin associated with the estimation of consent and surgery rates is 0.138, obtained at $p=0.5$. This suggests that CI around these estimates will be tight enough to provide meaningful guideline in the design of the larger trial. We will describe participant characteristics and evaluate reasons for protocol violations. We will calculate rates of dropout and other events, although we expect low numbers. Robust regression and non-parametric methods will be used for comparisons between randomized arms. The associations between pre-operative muscle strength (continuous or binary variable) with AV access primary outcome will be tested using logistic regression. The participants will be followed for a minimum of 12 months following index AV access placement. Participants who undergo AV access placement >90 days after randomization or who experience primary or secondary AV access failure will be analyzed as randomized in the intention-to-treat (ITT) analysis. Missing data will be handled under the missing at random (MAR) assumptions in compliance with an ITT protocol.²⁶ We will pay close attention to variables with higher rates of missingness, relative to others or display missingness patterns that deviate from the MAR assumptions since they could inform and guide the development of the larger trial. Results from the pilot analyses are likely to have high variability, but will provide valuable insight that will be considered in the design of a larger trial.

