Recruitment will be determined as the proportion of people meeting inclusion criteria who ultimately consent to randomization. We aim to consent $\geq 70\%$ of those eligible. Protocol adherence is based on the ability to undergo a graft or fistula surgery within 90 days of randomization, which we aim to attain in $\geq 70\%$ of participants. Outcomes of quality of life stratified by the type of first AV-access strategy. Changes in grip strength, pain related to the access (acute and chronic pain), patient's satisfaction with the access, changes in the level of independence (ADLs and IADLs) and HRQoL—will be compared between the two arms, with baseline (preoperative) assessments used as reference.

Subject Recruitment Methods

Clinical records of Wake Forest Nephrology practice, including WFOPD facilities, WFBMC nephrology outpatient clinics, and WFBMC nephrology inpatient service will be reviewed for eligibility. Study participants will be older adults of age ≥ 65 years with a diagnosis of incident ESKD or have advanced CKD expected to require HD initiation within 90 days of screening who meet the following additional inclusion criteria: (1) use a TCVC for HD, (2) did not undergo surgical creation of an AV access in the past, (3) are medically eligible to undergo surgery for AV access placement, and (4) are surgically eligible to undergo surgical placement of AVF and AVG. Medical eligibility for surgical placement of AV access will be determined as part of standard of care for patients with ESKD. In clinical practice, this aspect takes in consideration patient's clinical prognosis (e.g., unlikely to recover kidney function, medically stable to undergo surgical placement of AV access, anticipated life expectancy ≥ 9 months) and goals of care (HD is the intended long-term modality of treatment). Surgical suitability for placement of AV access, AVF and AVG, will be determined as part of standard of care by the vascular surgeon. To make this determination, the vascular surgeon will use the results of the ultrasound vascular mapping of both upper extremities. Patients who meet all the eligibility criteria will be approached by the vascular access coordinator, study coordinator, and/or PI for explanation of study participation.

Human Subjects Protection

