Appendix B : Assessment Instruments

Appendix C : Schedule of Assessments

Appendix D: Vascular access outcomes

Appendix E: Protocol Violation, Expected Events, Cause of Death

Appendix A: Study Flow Diagram

Appendix B: Assessment Instruments

- 1) **Grip Strength Test:** a muscle strength test that uses a hand-held dynamometer to assess the upper arm grip-strength in each arm. Study participant will squeeze the dynameter as hard as possible two separate times for each arm.
- 2) The four meter gait speed (4MGS) will be assessed on a flat, unobstructed four meter delineated course by trained research staff following a standard operating procedure. Participants will be asked to walk at their usual pace from a standing start. Two trials will be completed. The arithmetic mean of the two trials will be used for analysis. Participants will be allowed to use their usual walking aids and ambulatory oxygen, with the cylinder carried by an assistant and these factors will be kept constant within person measurements on repeated walk tests. To express gait speed in ms-1, distance walked (i.e. 4 meters) will be divided by time expressed in seconds.
- 3) **Short Form Vascular Access Questionnaire (SF-VAQ):** a questionnaire that the study participant will complete that measures the participant's satisfaction with their vascular access. Participant will circle a number on the scale that indicates their level of agreement with each statement regarding physical symptoms, social functioning, complications and overall satisfaction.
- 4) **Verbal Descriptor Scale (VDS):** a scale the study participant will complete that measures their pain at the AV access site. The participant will rate their pain as either absent/no pain, mild pain, moderate pain, or severe pain/pain as bad as could be/extreme pain.
- 5) **modified Abbey Pain Scale (mAPS) :** a scale used for people who cannot verbalize that measures their pain at the AV access site. The study staff will score the scale by observing the participant's vocalization, facial expression, and body language.
- 6) **Activities of Daily Living (ADL) and Instrumental Activities of Daily Living (IADL):** these two scales measure the level of independence of the study participant. For the ADL scale, study staff will ask participants how well they can perform various daily activities such as bathing, grooming, dressing, eating, etc.

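### Grip is tested in both hands, but the plan does not direct the analysis to the limb that receives the access and names no covariates

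*Combined protocol and SAP*

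**What the plan says.** Data Collection and Outcome Measure(s) sets the measurement rule: "The grip-strength test will be performed twice on each hand for each assessment and the mean of the two results will be used". Appendix B describes the same procedure, with the dynamometer squeezed "two separate times for each arm". Each grip assessment therefore gives four readings. Appendix C schedules grip at enrolment and in four later columns, the last of which applies only after primary access failure. The week 3 or 4 column is a clinical evaluation of the access, with no grip test marked.

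In the Analytical Plan, change in grip is one of several outcomes that "will be compared between the two arms, with baseline (preoperative) assessments used as reference". The methods named are robust regression and non-parametric comparison, with no covariates listed. Pre-operative strength, continuous or dichotomised, also enters a logistic regression for the access outcome. Neither use names a hand.

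The Objectives section gives the reason for measuring grip: the graft-first strategy "will limit upper extremity functional impairment from protracted access development" and from later access procedures. The access may go in either upper limb (Interventions and Interactions), and the site of the anastomosis is recorded.

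**The concern.** The hypothesis is about a limb, while the outcome as written is about a person. Four readings per assessment reduce naturally to two per-hand means, and nothing in the plan takes the step from two means to one value. Access hand, dominant hand, stronger hand and pooled hands all fit the wording, and they estimate different things. Because the access can be on either side, a dominant-hand or best-hand rule would sometimes analyse the unoperated limb.

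The gap also affects the predictor analysis. The weakness cut-offs (below 16 kg in women, below 26 kg in men) need one value per participant, and someone whose hands fall either side of the cut-off could be classed either way.

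Two things are at stake. The first is the effect and SD that the pilot passes to the larger trial. The second is that the hand could be chosen after the data are seen. Leaving out the access arm's own baseline and sex as covariates also gives up precision that is available from data already collected.

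**Working it through.** **The plan's only precision figure.** The Analytical Plan says: "The maximum uncorrected error margin associated with the estimation of consent and surgery rates is 0.138". With 50 participants (Sample Size), 1.96 × √(0.25/50) = 0.1386, which agrees with 0.138 apart from truncation. This concerns feasibility proportions. No effect size, SD, between-hand correlation or power is given for grip, so what follows is illustration on stated assumptions.

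**Set-up.** Let the change in grip have SD s in each hand, with correlation ρ between the two hands' changes. Let the strategy effect d act in the access hand only. Take 25 per arm and a two-sided 0.05 level, using normal theory. The effect detectable with 80% power in the access hand alone is (1.960 + 0.842) × √(2/25) = 0.79 s. For illustration d = 0.8 s, which gives 81% power.

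**If the wrong hand is sometimes analysed.** If a rule picks the access hand in a fraction q of participants, the average effect is q × d. The documents give no q.

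**If both hands are pooled (conditional worst case).** The effect is d/2 and the SD is s√((1+ρ)/2). The sample size relative to the access hand alone is ((1+ρ)/2) ÷ (1/2)² = 2(1+ρ).

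| ρ (assumed) | Standardised effect relative to access hand | Sample size multiple | Power at d = 0.8 s |
|---|---|---|---|
| 0 | 0.71 | 2.0 | 52% |
| 0.3 | 0.62 | 2.6 | 42% |
| 0.5 | 0.58 | 3.0 | 37% |
| 0.8 | 0.53 | 3.6 | 32% |

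**If the access hand is adjusted for the other hand's change.** The effect remains d only if strategy does not affect the other hand. The residual SD is s√(1−ρ²), equivalent to 1/(1−ρ²) times as many participants. Simple subtraction of the other hand has SD s√(2(1−ρ)), so it needs 2(1−ρ) times the sample size.

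| ρ (assumed) | Residual SD, adjusted | Equivalent participants, adjusted | Sample size multiple, subtraction |
|---|---|---|---|
| 0 | 1.00 s | 1.00 | 2.0 |
| 0.3 | 0.95 s | 1.10 | 1.4 |
| 0.5 | 0.87 s | 1.33 | 1.0 |
| 0.8 | 0.60 s | 2.78 | 0.4 |

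Subtraction loses precision whenever ρ is below 0.5. Adjustment costs about one degree of freedom at worst. These gains are measured against an unadjusted change. In a model that already holds the access arm's baseline grip and sex, the relevant quantity is the partial correlation given those terms, which cannot be worked out from the documents.

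**The case against.** The best reply is that this is a one-line clarification in a feasibility pilot. Feasibility is the stated principal aim, grip did not size the trial, the plan itself expects variable results, and robust regression does not rule out an access-hand analysis. That limits the severity. It does not supply the missing target or covariates, and grip appears in more columns of Appendix C than any other instrument except the two access-site scales, which share the same four later columns.

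Three stronger readings are tempting, and the documents do not support them.

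- A reader might infer that the plan averages the two hands and so halves the effect. The wording most naturally means two trials on one hand, and Appendix B treats gait speed in the same way, as the mean of two trials. Halving would also require an unaffected other hand.
- A reader might infer that the comparison confuses the local effect with general decline. The contrast is between randomised strategies, and "participants will be allocated with equal probability to either a graft-first (intervention) or fistula-first (comparator) strategy". Decline unrelated to strategy is balanced in expectation, so the other hand is not needed for validity.
- A reader might infer that the other hand's change should go into the main model as free precision. It is measured after randomisation. The Background suggests that longer and repeated procedures may erode strength and quality of life, so strategy could affect the other hand too. Appendix D lists creation of a new access as an outcome, and that access could be in the other arm.

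It is also fair to say that the remedy is not purely wording. No access side is recorded before randomisation, the side used could depend on the access type assigned, and a randomised participant who never has surgery has no access arm although analysis is by intention to treat.

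**Conclusion.** The concern holds in a limited form. Grip is measured in both hands at each grip assessment, yet the analysis neither targets the limb named by the hypothesis nor specifies covariates. That much rests on the text alone.

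The size of the loss depends on choices the plan leaves open. With the access hand analysed there is no dilution. With pooled hands and a purely local effect the loss reaches one half in kg, but only as a conditional worst case. The further gain from the other hand ranges from small to large across plausible correlations and cannot be promised.

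The change should be made, because the pilot is meant to inform a larger trial. The feasibility aims are not affected.

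**What to change.** - Define the outcome as the two-trial mean in the index-access arm at each scheduled grip assessment.
- Analyse it by robust regression on randomised strategy, with that arm's baseline grip and sex as covariates.
- Record the planned access side before randomisation. Use that side for the pre-operative predictor, including the weakness cut-off, and for participants who are never operated on. Tabulate how often the planned and actual sides differ.
- Report the contralateral-adjusted model, or the contralateral change on its own, only as a labelled supportive analysis. Flag or exclude assessments made after any new access in the other arm.

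**Cost.** No extra visits or grip tests are needed. The changes are analysis wording and one added data item, the planned side. The drawback of the supportive model is that its contralateral term is post-randomisation and may absorb part of a strategy effect, so it must not replace the main result.
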